6.3.6 Questionnaires

A health questionnaire will be administered at baseline to characterize the sample. Participants are asked whether a doctor or nurse ever told them that they have any of the following conditions: arthritis, asthma and/or other breathing problems, cancer (other than skin cancer), chronic skin problems, diabetes, heart disease, heart problems (other than heart disease), high cholesterol, hypertension or high blood pressure, mood problems or anxiety, multiple sclerosis, osteoporosis, parkinson’s disease, stroke, TIA/mini-stroke within last 18 months, mild cognitive impairment or memory impairment, neuropathy, or any other significant illness.

Participants’ expectations about the effects of intervention/control exercises on post-test outcomes will be examined as a potential covariate. During the last week of the intervention stage, the Trainers will administer a modified version of the The Cognitive Training Expectations questionnaire to examine participants’ attitudes and expectations about the effects of the intervention received on cognition and everyday function¹²². The NICT questionnaire was modified to refer to “music training” or “piano training”, and the “memory” and “reasoning” questions were omitted since we are not assessing these abilities. The questionnaire explains that cognitive function refers to abilities such as attention, memory, visual perception, information processing, and reasoning; and that cognitive training refers to activities that aim to improve cognitive functions by training within a specific timeframe (i.e., several weeks or months). The questionnaire then asks participants to rate what effects they expect the intervention exercises to have including whether the exercises will result in improved general cognitive function, memory, concentration, distractability, reasoning, multi-tasking, and everyday performance. Ratings are on a 7-point Likert scale ranging from completely unsuccessful (1), to no expectations (4), to completely successful (7). Participants also rate the degree to which the intervention was engaging, enjoyable, and challenging on a 7-point scale ranging from very strongly agree (7), to neither agree or disagree (4), to very strongly disagree (1). Finally, participants rate whether or not they were satisfied with the program ranging from extremely satisfied (7), to neither satisfied or dissatisfied (4), to extremely dissatisfied (1) and indicate whether they felt that they had “trained their brain” (yes/no). This questionnaire has been successfully implemented in others’ and our prior cognitive intervention studies.

At the baseline visit, a list of prescription medications that the participants’ are taking will be recorded. For those who score 20-25 on the MoCA who will be completing a clinical evaluation, the medication list will be provided for the study physician to review. At the clinical evaluation visit, the tester will review the list of medications with the participant and document any changes prior to the participant seeing the study physician. The study physician uses this information in the clinical diagnosis or exclusion of MCI.

A questionnaire will be administered at post-test to assess if any health-changes were experienced by the participants during the trial that could affect cognitive or functional performance. Participants are asked if they experienced any significant changes in health conditions such as head injury, chemotherapy or radiation treatment, heart attack or myocardial infarction, changes in vision or hearing, or underwent general anesthesia. They are also asked if they had any new diagnoses of stroke, mini-stroke, TIA, heart disease or congestive heart failure, Parkinson’s disease, mild cognitive impairment or memory impairment, Alzheimer’s disease, and Multiple Sclerosis.

7 MANAGEMENT OF ADVERSE EVENTS

We will track safety throughout the trial. Participants will be queried as to whether or not they experienced any discomfort at the end of each study visit. See **Reporting of Adverse Events** below for further details. Data and safety monitoring will focus on participant recruitment, data quality, and safety (confidentiality, minimization of risks, and surveillance for adverse events). The study team will meet weekly to discuss the progress of the trial. Details on adverse event monitoring and reporting are provided below.

An adverse event (AE) is defined as any unfavorable and unintended diagnosis, symptom, sign, syndrome or disease which either occurs during the study, having been absent at baseline, or if present at baseline, appears to worsen. Adverse events are to be recorded regardless of their relationship to the study intervention.

Participants may experience fatigue or frustration from completing the intervention exercises. Prolonged sitting activity can result in muscle/joint soreness (e.g., wrist, elbow, fingers, hip flexors, neck, back, buttock), eye strain, muscle cramping or stiffness, or headaches. Any of these symptoms that increase in frequency and last more than 24 hours after participating in intervention exercises will be considered an adverse event. The participant will be advised to seek treatment and not be continued until a physician clears such activity. Serious adverse effects from prior research of the interventions have not been reported.

A serious adverse event (SAE) is generally defined as any untoward medical occurrence that results in death, is life threatening, requires inpatient hospitalization or prolongation of existing hospitalization, results in persistent or significant disability/incapacity.

8 CRITERIA FOR PARTICIPANT DISCONTINUATION

Participants who undergo any surgical procedures requiring anesthesia, chemotherapy, or radiation during the study period will be excluded. Participants who experience a stroke, TIA, or head injury during the study period will be excluded. Participants who complete any other cognitive intervention not assigned to them during the course of the study will be excluded. In these situations, only data points collected prior to the event will be used in analyses. If plans to undergo such events are known, and 80% of assigned intervention sessions have been offered, an attempt to complete post-test prior to the event will be made.

9 STATISTICAL CONSIDERATIONS

9.1 General Design Issues

We will employ a randomized clinical trial design to accomplish the study objectives. Randomization will be stratified based on MCI status. Regardless of randomization or adherence, each eligible and enrolled participant will be encouraged to complete post-test. Participants may be followed longer with positive results and additional funding.

9.2 Primary Objectives

The primary and secondary outcome measures are detailed above.

9.2.1 Primary outcomes

- To examine the efficacy of piano training to improve CAP, cognition, and everyday function among older adults. We will assess the effects of piano training as compared to music listening instruction on CAP, cognition, and everyday function.

CAP includes Time Compressed Speech, Words-in-Noise, Dichotic Digits Test, Dichotic Sentence Identification and Adaptive Tests of Temporal Resolution. All are parametric tests of perception.

Cognition includes Verbal Fluency (phonemic, category, and switching), Digit Coding, and Trail Making test. All are parametric tests of cognitive function.

Everyday function includes the Timed IADL test and Test of Everyday Attention both parametric measures. Both measures will be examined individually.

Principal Component Analyses (PCA) will be performed with CAP, cognitive and functional measures to form composites of outcomes for use in analyses to reduce the number of comparisons.

Hypotheses: The piano training group will outperform the music listening instruction group on measures of CAP, cognition, and everyday function immediately post-intervention.

Secondary Objectives

The secondary objectives are:

- To examine the moderating effects of MCI on piano training efficacy. Moderating effects of MCI status will determine if piano training is effective for older adults with and/or without MCI. We do not have a directional hypothesis for this objective.
- To explore mediators of intervention effects.

Hypothesis: Grounded in theory⁸ and prior research⁹⁻¹¹, we hypothesize that piano training will improve CAP and cognitive performance, leading to functional improvements. We expect that enhanced CAP will mediate cognitive gains. We further hypothesize that cognitive gains will mediate functional improvements.

9.3 Sample Size

We expect up to 20% attrition after the initial in-person visit across the time period in which cognitive intervention study protocols will be administered. Our goal is to complete in-person screening visits for up to 450 participants in order to have up to 360 participants complete the study. We can tolerate higher rates of attrition. We require a minimum of 198 eligible participants with *at least* 99 individuals randomized to each condition (piano training, controls) to have adequate statistical power. With stratified randomization, this will result in *at least* 48 persons per MCI/no MCI subgroup.

Statistical power analysis using G*Power¹²³ in consideration of our pilot data effect sizes as well as attrition was conducted to estimate power. We will control type I error at .05 to achieve at least 80% statistical power.

To power **Specific Aim 1: To examine the efficacy of piano training to improve CAP, cognition, and everyday function among older adults**, a final n of 198 participants ($n=99$ per randomized condition) will achieve 95% power to detect a significant group x time interaction across baseline to immediate post-test, with an alpha of .05. This assumes a small effect size (f) of 0.10¹²⁴ (Cohen's f effect sizes are 0.10- small, 0.25- medium: f is roughly equivalent to $\frac{1}{2}$ of d when comparing two groups)¹²⁴.

To power **Specific Aim 2: To examine the moderating effects of MCI on intervention efficacy**, a final n of 168 will have .95 power at alpha .05 to detect medium effects ($f=.10$) for significant group x time x moderator three way interactions.

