Specific Aim 1: To examine the efficacy of piano training to improve CAP, cognition, and everyday function among older adults. We will compare changes in performance for piano training relative to control across the two measurement points (baseline, immediate post-test). We will use the PCA-derived composites of CAP and cognition, and everyday functioning as outcomes. We will use repeated measures analyses of variance within the mixed effects models, examining group as the between-subjects factor and time as the within-subjects factor. The group x time interaction will indicate whether the participants randomized to piano training change at differential rates over time relative to those randomized to the control group. This output will be obtained for each of the composite outcomes (CAP, cognition, and functional abilities). For aim 1 analyses and the composite outcomes of CAP, cognition, and everyday function, we will apply Holm-Bonferroni adjustments¹²⁵ to reduce Type I error. Specifically, the Holm-Bonferroni procedure uses a step-down process whereby p-values are sorted from lowest to highest, then the lowest p-value is used in its raw version, the second lowest p-value is multiplied by two, the third lowest p-value is multiplied by three and so on until the adjusted

p-value reaches or exceeds the pre-specified threshold for statistical significance, in our case a two-tailed p value of .05.

Intent-To-Treat Approach. We expect that some participants will not complete their intended followup according to the protocol for a variety of reasons, generating missing values. Intent-to-treat (ITT) analysis has become a widely accepted method for dealing with this issue. To maximize available information, we will employ statistical techniques that allow for the inclusion of missing data. Specifically, we will use linear mixed effects models to analyze data. This advanced analytical method allows for the inclusion of participants with missing data, so long as data are missing at random and offers flexibility with regard to the specification of the variance/covariance structure, which often leads to improved fit of the analytical model to the actual data. If there is non-ignorable missing data, we will apply pattern-mixture mixed effects models to assess the sensitivity of our findings with regard to missing data¹²⁶.

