Specific Aim 2: To examine the moderating effects of MCI on intervention efficacy. We will also test for moderation effects to determine at what stage along the cognitive status continuum—without MCI vs. MCI—intervention is most effective. To do so, we will examine three-way interactions (MCI x training group x time) for the CAP, cognitive, and everyday function composites. When an interaction is significant, we will stratify analyses by MCI status and examine effect sizes. Effect sizes from pre- to post- training relative to controls will be compared for participants with/without MCI. An alpha of .05 will be used for these analyses.

Participants who score 26 or higher on the MoCA will be defined as no MCI (i.e., cognitively normal). Those participants who score a 20-25 on the MoCA will be defined as MCI if they score a 0.5 on the CDR and have performance at or 1 SD below their age, sex, and education norms on any of the following measures: Trails, Verbal Fluency, Digit Coding, Craft Story Recall, Multilingual Naming Test, or Benson Complex Figure. Those with MoCA scores 20-25 who score 0 on the CDR, but have performance at or 1SD below expected for age, sex, and education will be adjudicated prior to analyses. If an individual scores 20-25 on the MoCA, and 0.5 on the CDR, but has performance above expected on all of the aforementioned measures, their case will be adjudicated prior to analyses. The study physicians will adjudicate such cases prior to coding of MCI status for final analyses.

To quantify the effects of piano training further, in addition to examining composite outcomes as detailed above, we will calculate and report effect sizes for pre-to-post change of piano training relative to controls for each individual measure of CAP, cognition, and everyday function for the sample overall as well as stratified by MCI status and among those who were adherent only (80% or more of sessions completed).

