In the primary analyses, we examined whether performance changed differentially by random assignment across composite outcomes from baseline to post-test as indicated by a significant group-by-time interaction. Covariates included hearing PTA, visual acuity, and expectations. The group-by-time interactions were not statistically significant for any of the outcomes ($ps > .194$). See Table 2. The results did not change when we included only those who were adherent ($ps > .180$). See Supplementary Table B. Piano training did not significantly enhance CAP, cognition, or everyday function as compared to music listening. We further examined if intervention effects varied by MCI status (Supplementary Table B). There were no significant group-by-time-by-MCI status interactions indicating those with and without MCI did not show differential benefit ($ps > .245$). Thus, MCI did not significantly moderate the effects of piano training.

Effect sizes for piano training as compared to music listening are shown in Table 3. Improvements were not evident in the primary analyses, adherent analyses, or the subsample without MCI on measures of CAP, cognition, or everyday function. Participants with MCI randomized to piano training showed potential small effect sizes for improvement relative to music listening on Trails A, Digit Symbol Coding, and one subtest of the TEA ($ds \geq 0.25$). Raincloud plots of individual assessment and composite variables are included in the supplemental materials.

Results indicated significant effects of time for ATTR in all models and significant effects of time for CAP in the primary and adherent analyses indicating improved performance from pre- to post- training. Significant effects of time were found for cognition and TEA in the primary and adherent analyses, indicating a tendency for decline across time. With respect to covariate effects, CAP, ATTR, and cognitive performance were significantly impacted by hearing. Similarly, Timed IADL and cognitive performance varied significantly by visual acuity. Those with poorer hearing or vision tended to perform worse on these outcomes. Interestingly,

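### Section 9.3 glosses f=0.10 as if it were d of about 0.20, but the stated 95% power with 198 participants reproduces only if f=0.10 means a 0.40 SD difference in change and the unstated pre-post correlation is about .70

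*Combined protocol and SAP*

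**What the plan says.** Section 9.3 (Sample Size) reports a G\*Power analysis made "in consideration of our pilot data effect sizes as well as attrition was conducted to estimate power". For Aim 1, a final n of 198 (99 per arm) "will achieve 95% power to detect a significant group x time interaction across baseline to immediate post-test, with an alpha of .05". The effect is called small, with f=0.10. A parenthesis then explains the scale: "f effect sizes are 0.10- small, 0.25- medium: f is roughly equivalent to" one half "of d when comparing two groups".

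For Aim 2, "a final n of 168 will have .95 power at alpha .05 to detect medium effects", again with f=.10.

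Section 9.6 confirms the Aim 1 test: a repeated-measures analysis "examining group as the between-subjects factor and time as the within-subjects factor", at a two-tailed .05. It also plans to report "effect sizes for pre-to-post change of piano training relative to controls for each individual measure of CAP, cognition, and everyday function". The note to Table 14.3 divides that relative change by the baseline SD. Section 9.5 (Interim Data Analyses) expects d of at least 0.25 relative to controls on at least one cognitive measure.

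Section 9.3 gives neither a pre-post correlation nor the G\*Power test and effect-size option. Section 6.3.5 lists test-retest values for single cognitive tests, from .51 (category switching) to .88 (phonemic fluency). It gives none for the composites and links none to the power calculation.

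**The concern.** The parenthesis has one job where it stands: to tell the reader how large f=0.10 is. The trial compares two groups, so the reader halves d, arrives at 0.20, and concludes that 198 people give 95% power for a 0.20 SD benefit. For a 2x2 group x time interaction the conversion is different, and the effect behind the 95% is twice that size.

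This matters for reading the result. Section 14 reports: "The group-by-time interactions were not statistically significant for any of the outcomes". If section 9.3 is taken at face value, that finding appears to make a 0.20 SD benefit very unlikely. The power calculation does not support that inference, nor the same inference for the d=0.25 of the interim rule.

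**Working it through.** **Inputs.** From section 9.3: N=198 (99 per arm), f=0.10, alpha .05. From section 9.6: a two-sided test of group x time with two groups and m=2 time points, so the F test has 1 and N−2=196 degrees of freedom. The pre-post correlation r is not given. I assume .5 to .8, which lies close to the range of the single-test reliabilities in section 6.3.5 but is not derived from them.

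**Step 1: reproduce the 95%.** G\*Power's default option for a within-between interaction uses the noncentrality λ = f²·N·m/(1−r) = 0.01 × 198 × 2/(1−r) = 3.96/(1−r).

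| r | λ | Power |
|---|---|---|
| .5 | 7.92 | 80.0% |
| .6 | 9.90 | 87.9% |
| .7 | 13.20 | 95.1% |
| .8 | 19.80 | 99.3% |

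At r=.70, N=196 gives 94.9% and N=198 gives 95.1%, so 198 is the smallest even total that reaches 95%. An r of about .70 is therefore the likely input, but this is back-solved and not stated.

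**Step 2: what f=0.10 means in that calculation.** Take a single-occasion SD of 1 and cell means of 0 and 0 (control, pre and post) and 0 and 0.4 (piano, pre and post). The grand mean is 0.1, the piano row mean is 0.2 and the post column mean is 0.2. The interaction residual in the last cell is 0.4 − 0.2 − 0.2 + 0.1 = 0.1, and all four residuals are ±0.1. Their root mean square over the SD is f = 0.10. So f is one quarter of the difference in change, and f=0.10 is 0.40 SD. A 0.20 SD difference in change is f=0.05.

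**Step 3: can the gloss and the 95% both hold?** If f is defined on change scores, then f = d/2 does hold with d in SDs of change, and f=0.10 is 0.20 of that SD. But then λ = f²·N = 0.01 × 198 = 1.98 and power is 28.8%. Two independent means at d=0.20 give the same λ and the same 28.8%. The readings under which the gloss is right give about 29%, and the reading that gives 95% makes the gloss wrong.

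**Step 4: power for smaller differences in change, default option, N=198.** The effects are in baseline SDs with f = d/4, so λ = (d/4)² × 396/(1−r), which is 0.99/(1−r) for 0.20 SD and 1.547/(1−r) for 0.25 SD.

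| r | 0.20 SD (f=0.05) | 0.25 SD (f=0.0625) |
|---|---|---|
| .5 | 29% | 42% |
| .7 | 44% | 62% |
| .8 | 60% | 79% |

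Power of 95% needs λ of about 13.13. For 0.20 SD that means 1−r = 0.99/13.13 = .075, so r is about .925. For 0.25 SD it means 1−r = 1.547/13.13 = .118, so r is about .88.

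**Check by simulation.** With 40,000 trials and 99 per arm, power at 0.40 SD was 80.3% (r=.5) and 95.0% (r=.7). At 0.20 SD it was 29.2% and 43.7%.

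**The case against.** The best defence is that the gloss, with its qualifier about comparing two groups, is a correct general statement about Cohen's benchmarks. The plan never writes d=0.20 and never claims power for 0.20 SD. That is true as far as it goes. But the parenthesis follows directly on the f=0.10 of the interaction and serves only to interpret it, and the trial does compare two groups, so the qualifier does not warn the reader off.

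A second defence is that 0.40 SD depends on an effect-size option the plan does not name. This stands. The 0.40 is a strong inference, because the alternatives tried give about 29%, but it should be worded as conditional until the sponsor confirms the option.

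A third is that the missing r is only missing detail, since 95% is reproducible at a plausible value and the plan's own criterion of at least 80% is met from r of about .5. This also stands. By itself the missing r would be a reporting gap.

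A fourth is that nothing in section 14 cites the power calculation, and Tables 14.2 and 14.3 give standard errors and effect sizes for interpreting the result. That is correct. The risk lies in later use of section 9.3.

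**Conclusion.** As written, section 9.3 invites a reading of its detectable effect that is too small by a factor of two. Under the option that reproduces its figure, 95% power applies to a 0.40 SD difference in change at r of about .70. For 0.20 SD it is about 29% to 60%, and for 0.25 SD about 42% to 79%, over r of .5 to .8. These figures rest on the assumed r, on G\*Power's default option, on 198 people with both measurements, and on taking the 0.25 of section 9.5 in baseline SDs. That 0.25 concerns single cognitive measures, whereas Aim 1 tests composites, so it is a benchmark and not a stated Aim 1 target.

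A reader might infer more, and the documents do not support it:

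- That the 95% is a miscalculation. It is correct at r of about .70.
- That the plan set out to detect 0.20 SD. It names f=0.10 and no d for Aim 1.
- That the trial misses its own power criterion. At f=0.10 it reaches 80% at r=.5 and more above that.
- That Aims 1 and 2 used conflicting correlations. The Aim 2 settings are not given, so any r solved from n=168 rests on guesses. What is visible is that f=.10 is called small for Aim 1 and medium for Aim 2.

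**What to change.** 1. Delete the half-of-d gloss, or replace it with the conversion that applies to the interaction under the option used.
2. State the G\*Power test, the effect-size option, the r entered and its source.
3. Restate the power as conditional on these. If the default option is confirmed, wording could be: with a final n of 198 (99 per arm), two-sided alpha .05 and a pre-post correlation of [r, source], power is [x]% for a group x time interaction of f=0.10, that is, a between-arm difference in change of 0.40 baseline SD. At r of about .70 the figure is 95%. A short table over r would help.
4. Do not cite section 9.3 as showing 95% power for a 0.20 or 0.25 SD benefit.
5. For Aim 2, state the settings and r used, and reconcile calling f=.10 medium there with small in Aim 1.

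The cost is text only. Design, analysis and participant numbers do not change. The one downside is a less favourable-looking power statement.

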1.5 Interventions and Duration

Piano Training. Piano training will consist of basic piano technique, dexterity exercises, piano literature, and music theory. At each bi-weekly training session, participants will be trained in groups and will be expected to

perform all technique (scales/finger dexterity exercises), piano repertoire (Alfred Basic All-in-One Method), and complete music theory assignments. Each class session will be structured with a short review followed by an intense focus on new skill development (e.g., scales; chord progressions) and concept formation (e.g., intervals). At least one five-minute break will occur in each session.

Music Listening Instruction Condition. Participants randomized to the music listening instruction condition will engage in music listening and appreciation. The participants read about, listen to, view diagrams of, and answer questions about the music. Each lesson will cover chapters from *Music Listening Today* over 90 minutes. Each lesson will be structured as follows: Overview of chapter material and group listening activity, participants read over chapter on their own, active listening activity, five question quiz, overview of next chapter material and group listening activity, participants read over chapter on their own, active listening activity, and five question quiz. At least one five-minute break will occur in each session. This structure is equivalent to the switching between ensemble/individual approach to teaching in the piano training condition.

The two training conditions will be equivalent in terms of frequency and duration of each session (90 min/day, two days/wk, 10 weeks) and social contact (led by trainer and conducted in groups of up to 10 persons). Both conditions will be described as “music training”.

Sample Size and Population

Our goal is to have up to 360 participants complete the study. Individuals with normal cognition and those with a clinical diagnosis of MCI will be recruited for this study. Inclusion and exclusion criteria are detailed below.

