5.5 Describe the procedure for obtaining intervention group assignment

The study coordinator with the statistician will randomize participants stratified by MCI status. Participants with and without MCI will be randomized in a 1:1 ratio to either piano training or the active control condition of music listening instruction. To ensure balance throughout enrollment, randomization will be stratified by MCI status (present vs. absent) and conducted in varying blocks of participants as designed by Co-I Ji. [name] will generate the stratified permuted random blocks using R. [name] will maintain the random seed and the computer codes and will send the randomization list to the clinical trial coordinator. The treatment allocation will be denoted as A or B and recorded on the randomization form by the clinical trial coordinator. The study coordinator will control access to the randomization list and know whether A (B) stands for intervention (control). Study investigators [name], [name], and [name] will remain blind to participant condition. The testers will remain blind to participant condition. The trainers (including Co-I [name]) and clinical trial coordinator will be aware of participants' randomized condition.

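### Section 9.3: at one pre-post correlation 198 and 168 are not both the n required for 95% power at f=.10, f=.10 is mislabelled as medium, and the floor of 48 per subgroup does not follow from stratification

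*Combined protocol and SAP*

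**What the plan says.** Section 9.3 sets a general target: "We will control type I error at .05 to achieve at least 80% statistical power". For Aim 1 it states that 198 participants, 99 per arm, give 95% power for the group x time interaction at f=0.10, which it calls small. For Aim 2 it states that "a final n of 168 will have .95 power at alpha .05 to detect medium effects", with f=.10 in brackets, for the group x time x moderator interaction. The paragraph on Aim 1 supplies the scale: "f effect sizes are 0.10- small, 0.25- medium: f is roughly equivalent to" half of d for two groups.

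The section names G*Power but gives no correlation between baseline and post-test. It also says that stratified randomisation of at least 99 per arm will yield at least "48 persons per MCI/no MCI subgroup".

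Section 5.5 describes the allocation: "randomization will be stratified by MCI status (present vs. absent) and conducted in varying blocks", at 1:1 within each stratum. Section 1.5 says only this about the mix: "Individuals with normal cognition and those with a clinical diagnosis of MCI will be recruited for this study". Section 9.6 defines the Aim 2 test: "we will examine three-way interactions (MCI x training group x time"), each factor having two levels.

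**The concern.** Power for a two-occasion interaction depends heavily on the pre-post correlation, and the three-way contrast should not need fewer people than the two-way one at the same f, alpha and power. Yet the stated n falls from 198 to 168. A reader cannot reproduce both figures from one set of inputs.

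The word *medium* makes the Aim 2 sentence harder still to read, and the subgroup sentence presents a number as a product of randomisation when it depends on who is recruited. Moderation by MCI is a secondary objective. At stake is whether the stated 95% tells a reader anything definite about how well that objective was powered.

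**Working it through.** **Inputs.** From section 9.3: alpha .05, f=.10, power .95, n=198 with two groups and n=168. From section 1.3: two occasions, m=2. From section 9.6: MCI (2) x group (2) x time (2), so the three-way term has (2-1)(2-1)(2-1) = 1 df. The correlation r is not in the documents; it is an assumption and is shown as a range.

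**Formula.** Noncentral F for a within-between interaction: lambda = f² x N x m / (1 - r), with numerator df 1 and denominator df N - k, where k=2 for Aim 1 and k=4 for Aim 2.

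**Step 1: reproduce Aim 1.** At r=.70, lambda = .01 x 198 x 2 / .30 = 13.2 on (1, 196) df, and power is 95.1%. The required n is exactly 198. At r=.50, lambda = 7.92 and 198 gives only 80.0%. So the Aim 1 figure implies r of about .70.

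**Step 2: Aim 2 at the same r.** With N=168, lambda = .01 x 168 x 2 / .30 = 11.2 on (1, 164) df, and power is 91.4%. For 95% the requirement is 200; this differs from 198 only because it is rounded to four equal groups.

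**Step 3: required n for 95% power over r.**

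| r | Aim 1 (two groups) | Aim 2 (four groups, 1 df) |
|---|---|---|
| .50 | 328 | 328 |
| .60 | 262 | 264 |
| .70 | 198 | 200 |
| .745 | 168 | 168 |
| .75 | 166 | 168 |
| .80 | 132 | 132 |

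Apart from rounding, the two columns agree at every r. The figure 168 appears for Aim 2 only at r of about .745 to .75, and there Aim 1 needs 166 to 168, not 198. Reading f as .25 does not rescue 168: the 95% requirement on 1 df would then be 108 at r=0 and 56 at r=.5.

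**Step 4: both sentences as floors.** At r=.745, 198 gives 97.5% and 168 gives 95.0%; at r=.75, 97.7% and 95.4%. Both power statements are then true, with 198 more than Aim 1 needs for 95%.

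**Step 5: f=.10 in SD units.** The standard error of the three-way contrast in baseline-SD units is sqrt(2(1 - r) x sum of 1/n over the four cells). With four cells of 49.5 and r=.70 this is sqrt(0.60 x 0.0808) = 0.220. A difference of 0.80 SD gives 0.80/0.220 = 3.63, and 3.63² = 13.2, the lambda of Step 1. So with equal cells f=.10 is a 0.80 SD difference in piano effect between strata. The same matching gives 0.40 SD for the two-way term.

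**Step 6: the floor of 48.** If 48 is an arm-by-MCI cell, four cells need 4 x 48 = 192 of 198, so close to half the sample must have MCI (at least 96 people). If 48 is a whole stratum, an MCI share of 48/198 = 24% is enough. In Table 14.1 the female counts and percentages imply about 37 MCI participants in the piano arm (18/.48 = 37.5) and 39 in the listening arm (17/.44 = 38.6), about 76 in all. Table 14.3 analyses 52 with MCI and 146 without. The cell reading was not met on either count; the stratum reading was met on both.

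**Step 7: power for 0.80 SD at N=198** (1-df contrast, noncentral t, 194 df, equal arms within strata assumed).

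| r | equal cells | 52/146 split |
|---|---|---|
| .5 | 80% | 69% |
| .7 | 95% | 89% |
| .8 | 99% | 97% |

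With the 52/146 split, 95% needs r of about .77.

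**The case against.** The strongest reply is that neither sentence calls its n the smallest that gives 95%. Both are power statements, set beside a general target of at least 80%, and for the planned 1-df contrast both are true at any r of about .745 or more. That stands. A reader might infer that either 168 or .95 must be an error; the documents do not support this, because r is missing and a single r exists at which both sentences hold. What remains is that the two figures are not both requirements under one r, and that neither can be checked as printed.

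A reader might also notice that a four-group test on 3 df at 80% power and r=.70 needs exactly 168, and conclude that this is what was run. That is conjecture about software inputs nobody outside the study has seen, and it would not be the contrast that section 9.6 plans.

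It is also fair to say that 52 is the analysed MCI count, whereas the sentence about 48 concerns people randomised. Table 14.1, with about 76, is the nearer comparator. On it the stratum reading is met comfortably and the cell reading is missed by less. The wording point is untouched: 1:1 allocation within strata balances the arms and says nothing about how large each stratum will be.

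Finally, Aim 2 is secondary and has no directional hypothesis, and effect sizes by MCI status are reported. This limits the consequence.

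**Conclusion.** The point holds as a minor one, in three parts.

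- **Sample sizes.** Section 9.3's 198 and 168 are not both the n required for 95% power at f=.10 under one correlation. At the r that yields 198 (about .70), 168 gives about 91%. Which figure is off, if either, cannot be determined from the documents.
- **Label.** Calling f=.10 medium contradicts the section's own scale. This needs no assumption.
- **Subgroup floor.** The minimum of 48 is ambiguous and is not delivered by the design on either reading.

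A reader might go further and infer that the trial was too small for Aim 2. The documents do not show that: 198 exceeds 168, and with equal cells 198 gives about 95% for f=.10 at r=.70. That reassurance depends on an MCI share the plan never set; at the analysed 52/146 split the figure is about 89% at r=.70. These results rest on the noncentral F and t formulas shown, on r taken as a range, and on equal arms within strata.

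**What to change.** Enter a dated clarification to section 9.3, since data collection is complete.

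1. State one r for both aims and the 1-df contrast of section 9.6, and restate the Aim 2 power to match. For example, at r=.70 with equal cells, 168 gives about 91% and 198 about 95%.
2. Delete the word *medium* and give the detectable difference in SD units: 0.80 SD between strata at f=.10 with equal cells.
3. Say whether 48 means whole MCI strata or arm-by-MCI cells. Replace the claim that randomisation produces it with an MCI share labelled as an assumption, and state Aim 2 power as conditional on that share.

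The cost is wording and a few recomputed figures; no extra participants are needed. The downside is that the stated Aim 2 power becomes conditional on r and the MCI share, and may look less favourable than 95%.
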